Overall Rationale for the Amendment: The overall rationale for the changes implemented in the protocol amendment was to include an additional urine pregnancy test at Week 48 of the study, increase the percentage of total participants who are in Hurley Stage III, make necessary corrections to the total blood volume to be collected from each participant during the study, eliminate certain laboratory tests identified as not needed, resolve inconsistencies identified in the duration of continued contraception after the subject receives their last dose, and other minor typographical issues.

Section number and Name	Description of Change	Brief Rationale
1.1 Synopsis	Added the following word where indicated:	Included the word "activity" to be
Objectives and Endpoints Other Secondary Endpoints	• The proportion of participants with HS-IGA (investigator's global assessment) score of inactive (0), almost inactive (1), or mild activity (2) and with at least 2-grade improvement relative to baseline at Week 16.	consistent with terminology used in the HS-IGA assessment tool.
	• The proportion of participants with HS-IGA score of inactive (0) or almost inactive (1) at Week 16 among participants with HS-IGA score of moderate activity (3) or severe activity (4) at baseline.	
1.1 Synopsis	Added the following text: "If a given comparison is	Provide clarification of multiple
Efficacy Analyses	not significant at the 2-sided α level of 0.05, nominal p values will be provided for the	testing procedure.
	subsequent treatment group comparisons and the	
	subsequent treatment group comparisons will be	
	considered as supportive."	
1.3 Schedule of	Included an additional urine pregnancy test to be	Added based on health authority
Activities	performed at Week 48 or at early termination	feedback.
Study Procedures	visit.	
Urine pregnancy test 3. Objectives and	Added the following word where indicated:	Included the word "activity" to be
Endpoints		consistent with terminology used in
Other Secondary Endpoints	The proportion of participants with HS-Investigator's Global Assessment (HS-IGA) score of inactive (0), almost inactive (1), or mild activity (2) and with at least 2-grade improvement relative to baseline at Week 16.	the HS-IGA assessment tool.
	The proportion of participants with HS-IGA score of inactive (0) or almost inactive (1) at Week 16 among participants with HS-IGA score of moderate activity (3) or severe activity (4) at baseline.	
4.2.1. Study-Specific	Revised the amount for the total blood volume in the	The total blood volume to be
Ethical Design Considerations	following sentence: "The total blood volume to be	collected from each participant in
Considerations	collected from each participant in each group	each group over the course of the

Section number and Name	Description of Change	Brief Rationale
and Ivanic	(approximately 150—approximately 181.5 mL over approximately 48 weeks) is far less than the American Red Cross standard limit for whole blood donation (approximately 475 mL q8w) and is therefore considered an acceptable amount of blood to be collected over this time period."	study was updated.
5.1 Inclusion Criteria Criterion #16a	Corrected to the appropriate units: a. Hemoglobin 10 g/dL (SI: 100 g/Lmmol/L)	Editorial correction: SI units corrected to mmol/L.
6.3 Measures to Minimize Bias: Randomization and Blinding Intervention Allocation Procedures for Randomization and Stratification	Revised the percentage provided in the following sentence: "Additionally, the number of participants in Hurley stage III should be limited to approximately 30% 50% of the total planned number of participants."	The percentage of participants in Hurley stage III out of the total number of study participants was increased due to fewer than expected subjects with Hurley stage I status screened or randomized at the time of this protocol amendment.
6.5.5. Prohibited Therapy	 Added some clarification text to the following bullets: Concomitant use of oral antibiotic therapy for HS or inflammatory disorders. Systemic antibiotic use (including oral) is allowed for the treatment of acute infections such as bacterial, viral, or fungal. Oral or injectable corticosteroids for the treatment of HS, except for protocol allowed intralesional rescue therapy as outlined in Section 6.5.1. 	Clarification related to the prohibited therapy.
6.5.6 Concomitant Corticosteroid use for Conditions Other than HS	Added a new section regarding Concomitant Corticosteroid use for Conditions Other than HS. The use of systemic corticosteroids for indications other than HS should be limited to situations for which, in the opinion of the treating physician, there are no adequate alternatives. They should be used on a short-term basis, preferably for ≤2 weeks. Longer-term use of corticosteroids should be discussed with the medical monitor or designee and may require discontinuation of study drug. Inhaled, otic, ocular, nasal or other routes of mucosal delivery of corticosteroids are allowed throughout the study.	Clarification related to the Concomitant Corticosteroid use for Conditions Other than HS
8. Study Assessments and Procedures Blood Sample Collection 8.2.4 Clinical Safety Laboratory Assessments	Revised the amount for the total blood volume in the following sentence: "The total blood volume to be collected from each participant through Week 48 of the study will be approximately 150 approximately 181.5 mL." Added the following information to the end of the sentence: "Female participants of childbearing potential will undergo a urine pregnancy test at	The total blood volume to be collected from each participant over the course of the study was updated. Added based on health authority feedback.
	screening, before each study intervention administration, and at the Week 48 or early termination visit."	

Section number and Name	Description of Change	Brief Rationale
9.4.1 Statistical Method	Added the following sentence: "In case the number of subjects that are Hurley Stage I at baseline is much less than was expected, subjects that were Hurley Stage I will be pooled with-subjects that were Hurley Stage II at baseline when baseline Hurley Stage is adjusted for in analyses."	New text added due to few Hurley I subjects screened or randomized at the time of this protocol amendment.
9.4.2.1 Primary Analysis	Deleted text where indicated: "To address the primary objective, a CMH chi-squared statistic stratified by baseline weight (≤95 kg, >95 kg) and baseline Hurley stage (I, II, and III) at an alpha level of 0.05 will be used for each of the following hypotheses:"	Text deleted since Hurley Stage I and II could be pooled in the analyses. This was already clarified in Section 9.4.1.
9.4.2.2 Major Secondary Analyses	Added the following text: "With the sequential analyses specified above within each dose group vs placebo, each of the hypotheses will be tested at a 2-sided α level of 0.05 provided that the significance is achieved for the preceding hypothesis test in the specified order shown in Figure 2. If a given comparison is not significant at the 2-sided α level of 0.05, nominal p values will be provided for the subsequent treatment group comparisons and the subsequent treatment group comparisons will be considered as supportive."	Provided clarification of multiple testing procedure.
9.4.2.3 Other Efficacy Analyses	 Added the following word where indicated: The proportion of participants with HS-IGA score of inactive (0), almost inactive (1), or mild activity (2) and with at least 2-grade improvement relative to baseline at Week 16 will be compared between each of the guselkumab groups and the placebo group. The proportion of participants with HS-IGA score of inactive (0), almost inactive (1) at Week 16 among participants with HS-IGA score of moderate activity (3) or severe activity (4) at baseline will be compared between each of the guselkumab groups and the placebo group. 	Included the word "activity" to be consistent with terminology used in the HS-IGA assessment tool.
9.4.3 Safety Analyses Adverse Events	Modified the following text: • The incidence and type of AEs temporally associated with infusion (defined as an AE that occurred on the same day of infusion, with a start time during infusion or ≤ 60 minutes after the end of infusion). infusion reactions.	Clarified the definition of AEs temporally associated with infusion of study intervention.
10.3 Appendix 3: Clinical Laboratory Tests Protocol-Required Safety Laboratory Assessments Other Laboratory Tests	The following tests were deleted: • serum antibody titers to varicella, measles, mumps, and rubella) • Serum IgG, IgM, IgA levels	Laboratory tests identified as not performed were deleted.
10.7 Appendix 7: Contraceptive and Barrier Guidance and Collection of	Changed the text as follows: "As noted in Inclusion Criterion 8, study participants who are women of childbearing potential must be practicing a highly effective method of contraception and remain on a	The duration of continuing to practice contraception after receiving the last dose of study intervention was changed to

Section number and Name	Description of Change	Brief Rationale

1. PROTOCOL SUMMARY

1.1. Synopsis

A Phase 2, Multicenter, Randomized, Placebo-Controlled, Double-Blind, Proof-of-Concept Study to Evaluate Guselkumab for the Treatment of Subjects with Moderate to Severe Hidradenitis Suppurativa

Protocol number: CNTO1959HDS2001

Guselkumab (CNTO 1959) is a fully human immunoglobulin G1 lambda ($IgG1\lambda$) monoclonal antibody that binds to the p19 protein subunit of human interleukin (IL)-23 with high specificity and affinity. The binding of guselkumab to the IL-23p19 subunit blocks the binding of extracellular IL-23 to the cell surface IL-23 receptor, inhibiting IL-23-specific intracellular signaling and subsequent activation and cytokine production. Guselkumab has been studied in Phase 1, Phase 2, and ongoing Phase 3 studies for the treatment of moderate to severe plaque psoriasis in adults. Guselkumab has been approved for the treatment of adults with moderate to severe plaque psoriasis in the United States, Europe, Canada, and several other countries. Guselkumab is also being studied globally for the treatment of psoriatic arthritis (PsA), Crohn's disease, and pediatric psoriasis.

OBJECTIVES AND ENDPOINTS

Objectives

Primary Objective

The primary objective of this study is to evaluate the initial efficacy, safety, and tolerability of guselkumab in adult participants with moderate to severe hidradenitis suppurativa (HS).

Secondary Objectives

The secondary objectives of this study are:

- To evaluate the efficacy of guselkumab in adult participants with moderate to severe HS during the maintenance phase.
- To evaluate the effect of guselkumab on the dermatologic health-related quality of life in adult participants with moderate to severe HS.
- To evaluate the pharmacokinetics (PK), immunogenicity, and pharmacodynamics (PD) of guselkumab therapy in adult participants with moderate to severe HS.

Endpoints

Primary Endpoint

The proportion of participants achieving Hidradenitis Suppurativa Clinical Response (HiSCR) at Week 16

Major Secondary Endpoints

- The change from baseline in total abscess and inflammatory nodule (AN) count at Week 16.
- The change from baseline in Dermatology Life Quality Index (DLQI) score at Week 16.
- The change from baseline in HS-related pain in the past 24 hours based on Hidradenitis Suppurativa Symptom Diary (HSSD) at Week 16.

Other Secondary Endpoints

- The proportion of participants achieving at least 50%, 75%, 90%, and 100% reduction in total AN count at Week 16.
- The proportion of participants achieving an AN count of 1 and 2, respectively, at Week 16.
- The proportion of participants achieving complete elimination of abscesses at Week 16 among those participants with abscesses at baseline.
- The change from baseline in the number of abscesses at Week 16.
- The change from baseline in HSSD symptom scale score (other than pain the past 24 hours) at Week 16.
- The change from baseline in HSSD total symptom score at Week 16.
- The proportion of participants achieving complete elimination of draining fistulas at Week 16 among those participants with draining fistulas at baseline.
- The change from baseline in number of draining fistulas at Week 16.
- The proportion of participants achieving complete elimination of inflammatory nodules at Week 16 among those participants with inflammatory nodules at baseline.
- The change from baseline in number of inflammatory nodules at Week 16.
- The proportion of participants with HS-IGA (investigator's global assessment) score of inactive (0), almost inactive (1), or mild activity (2) and with at least 2-grade improvement relative to baseline at Week 16.
- The proportion of participants with HS-IGA score of inactive (0) or almost inactive (1) at Week 16 among participants with HS-IGA score of moderate activity (3) or severe activity (4) at baseline.
- The change from baseline in Hospital Anxiety and Depression Scale (HADS) scores at Week 16.
- The change from baseline in high-sensitivity C-reactive protein (hs-CRP) at Week 16.
- The distribution of the Patient Global Impression of Change (PGIC) of HS severity at Week 16.

Hypotheses

The primary hypothesis is that guselkumab treatment is superior to placebo as assessed by the proportion of participants achieving HiSCR at Week 16.

The major secondary hypotheses are that guselkumab treatment is:

- Superior to placebo as assessed by the change from baseline in AN count at Week 16.
- Superior to placebo as assessed by the improvement in patient-reported outcomes (PRO) as measured by:
 - The change from baseline in DLQI score at Week 16.
 - The change from baseline in HS-related pain in the past 24 hours based on HSSD at Week 16.

OVERALL DESIGN

This is a Phase 2, multicenter, randomized, placebo-controlled, double-blind study evaluating the efficacy, safety, PK, and immunogenicity of subcutaneous (SC) and intravenous (IV) administered guselkumab for the treatment of moderate to severe HS in adult participants. The participant population will comprise men and women who have had moderate to severe HS for at least 1 year.

Two database locks (DBLs) are planned for this study at Week 16 and Week 48, respectively. An interim analysis will be conducted when a subset of participants have completed the Week 16 visit.

An independent Data Monitoring Committee (DMC) will be commissioned for this study for safety evaluation.

NUMBER OF PARTICIPANTS

180 participants, \geq 18 years of age, with HS, that is moderate to severe, and has been present for at least 1 year before the first administration of study intervention, and stable for at least 1 month (28 days) prior to screening as determined by the investigator through patient interview and/or review of the medical history. Participants must also have HS lesions in at least 2 distinct anatomic areas, had an inadequate response to an adequate course of oral antibiotics for treatment of HS in the investigator's opinion, and have a total AN count of \geq 3 at the screening and baseline visits. Participants must agree to daily use of soap and water, or a topical antiseptic wash containing chlorhexidine gluconate, triclosan, or benzoyl peroxide, or a dilute bleach bath to all areas affected by HS throughout the study.

INTERVENTION GROUPS AND DURATION

All participants will be randomized in a 1:1:1 ratio to 1 of 3 treatment groups as described below:

Group 1: Guselkumab Regimen 1 (1200 mg IV q4w x 3 \rightarrow 200 mg SC q4w)

Participants will receive guselkumab 1200 mg IV at Week 0, Week 4, and Week 8 (ie, a total of 3 IV guselkumab doses and 3 SC placebo doses). At Week 12, participants will continue treatment with guselkumab 200 mg SC q4w through Week 36.

Group 2: Guselkumab Regimen 2 (200 mg SC q4w x 3 \rightarrow 200 mg SC q4w)

Participants will receive guselkumab 200 mg SC at Week 0, Week 4, and Week 8 (ie, a total of 3 SC guselkumab doses and 3 IV placebo doses). At Week 12, participants will switch treatment to guselkumab 200 mg SC q4w through Week 36.

Group 3: Placebo

Participants will receive placebo IV and SC at Week 0, Week 4, and Week 8 (ie, a total of 3 IV and 3 SC placebo doses) and an additional SC placebo dose at Week 12. At Week 16, participants will be rerandomized at a 1:1 ratio to either guselkumab 200 mg SC q4w through Week 36 or guselkumab 100 mg SC at Weeks 16, 20, 28, 36 and placebo at Weeks 24 and 32.

A screening period will take approximately 4 weeks. All participants will enter safety follow-up after Week 36 through Week 48.

EFFICACY EVALUATIONS

Efficacy evaluations include:

- HS-Investigator's Global Assessment
- Lesion Counts
- Hurley Staging
- HSSD
- DLQI

- HADS
- PGIC of HS Severity
- Photographs of HS lesions

PHARMACOKINETIC AND IMMUNOGENICITY EVALUATIONS

Venous blood samples will be collected for the measurement of serum guselkumab concentrations and detection of antibodies to guselkumab at the time points presented in the Schedule of Activities. Serum samples will also be collected at the final visit from participants who terminate study participation early.

BIOMARKER EVALUATIONS

Biomarker assessments will include the evaluation of relevant markers in serum for all participants and will be collected at the time points presented in the Schedule of Activities.

Serum samples will be analyzed for circulating factors such as cytokines and other inflammatory markers (eg, IL-17A, IL-17F, IL-23, TNF α , IL-6, IL-22), and other categories of biomarkers potentially associated with the development and progression of HS or related to the guselkumab mechanism of action.

SAFETY EVALUATIONS

Safety evaluations conducted at each study visit will include the assessment of adverse events (AEs, at the visit and those occurring between evaluation visits), a tuberculosis evaluation and other infection assessment, clinical laboratory blood tests (complete blood count and serum chemistries), physical examinations, vital sign measurements, echocardiogram, suicidality assessment measured using C-SSRS, concomitant medication review, and observations for injection-site reactions, reactions temporally associated with an infusion, and/or allergic reactions.

STATISTICAL METHODS

Sample Size Determination

This study is designed to enroll approximately 180 participants, in order to have sufficient power achieving the primary efficacy endpoint. The assumptions for the sample size and power calculations were based on the clinical data from the 2 adalimumab (Humira®) Phase 3 clinical studies M11-313 (PIONEER I) and M11-810 (PIONEER II) that evaluated the safety and efficacy of adalimumab in the treatment of adult participants with moderate to severe HS. With 60 participants in each of the guselkumab treatment group and 60 participants in the placebo group, there will be more than 90% power to detect a treatment difference of 30% between each guselkumab group and the placebo group for the primary efficacy endpoint with a significance level of 0.05.

Efficacy Analyses

All randomized participants who received at least 1 dose of study intervention will be included in the efficacy analyses. Participants will be analyzed according to the treatment group to which they were randomized, regardless of the treatment they actually received.

For response efficacy endpoints, treatment comparisons will be performed using a Cochran-Mantel-Haenszel (CMH) test stratified by the baseline weight (≤95 kg, >95 kg) and baseline Hurley stage (I, II, and III). For continuous efficacy endpoints, treatment comparisons will be performed using either a Mixed-Effect Model Repeated Measure (MMRM) model or an analysis of covariance (ANCOVA) model. All of the models will have treatment group, baseline weight (≤95 kg, >95 kg), baseline Hurley stage (I, II, and III), and baseline value as explanatory factors. MMRM models will additionally include visit, treatment by visit, and baseline value by visit interaction terms. All statistical tests will be performed at a

12

2-sided significance level of α =0.05. In addition, graphical data displays (eg, line plots) and participant listings may also be used to summarize/present the data.

In order to control the overall Type 1 error rate for comparisons between each guselkumab group and the placebo group, the primary analysis and major secondary analyses will be tested in a fixed sequence for the comparisons at an alpha level of 0.05. If a given comparison is not significant at the 2-sided α -level of 0.05, nominal p values will be provided for the subsequent treatment group comparisons and the subsequent treatment group comparisons will be considered as supportive.

[figure not shown]
Analyses for other efficacy endpoints will be performed and nominal p-values will be provided.

Safety Analyses

Safety data, including but not limited to, AE, serious adverse events (SAE), infections, serious infections, mortality, suicidality assessment, changes in laboratory assessments, and changes in vital signs will be summarized. Intervention-emergent AEs will be summarized by treatment group and Medical Dictionary for Regulatory Activities (MedDRA) system organ class and preferred terms.

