9.2. Sample Size Determination

This study is designed to enroll approximately 180 participants, primarily in order to provide adequate information to have sufficient power for the primary efficacy endpoint. The rationale for the study sample size is based on the hypothesis tests for the primary efficacy endpoint.

Two adalimumab (Humira®) Phase 3 clinical studies have been conducted to evaluate the safety and efficacy of adalimumab in the treatment of adult participants with moderate to severe HS. The response rates observed in Study M11-313 (PIONEER I) and M11-810 (PIONEER II) for HiSCR at Week 12 were 42% vs 26% and 59% vs 28% in the adalimumab weekly group and placebo group, respectively.

Therefore, the assumptions to calculate sample size and power shown in Table 1 are:

- The proportion of placebo participants achieving HiSCR at Week 16 is approximately 25%
- The difference between guselkumab treatment group and placebo group on proportion of participants achieving HiSCR at Week 16 is approximately 30%

Based on the above assumptions, with 60 participants in each of the guselkumab treatment group and 60 participants in the placebo group, there will be more than 90% power to detect a treatment difference of 30% with a significance level of 0.05.

Table 1:	Statistical Power for the HiSCR Response Rate Comparing to Placebo at Week 16						
	Treatment group	Sample size	HiSCR	Δ (difference)	Power		
1	Placebo	60	20%	25%	85%		
	Guselkumab	60	45%	2370			
2	Placebo	60	20%	200/	94%		
	Guselkumab	60	50%	30%			
3	Placebo	60	20%	35%	98%		
	Guselkumab	60	55%	33%			
4	Placebo	60	25%	250/	82%		
	Guselkumab	60	50%	25%			
5	Placebo	60	25%	200/	93%		
	Guselkumab	60	55%	30%			
6	Placebo	60	25%	250/	98%		
	Guselkumab	60	60%	35%			
HiSCR=Hidradenitis Suppurativa Clinical Response							

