9.4.2. Efficacy Analyses

9.4.2.1. Primary Analysis

The primary efficacy endpoint is the proportion of patients with a clinical response at Week 16, defined according to the HiSCR measure as at least a 50% reduction from baseline in the total abscess and inflammatory- nodule count, with no increase in the abscess or draining fistula count.

In the primary efficacy analysis, data from all randomized participants who received at least 1 administration of study intervention will be analyzed according to their assigned treatment group. Participants who meet treatment failure criteria prior to Week 16 will be considered nonresponders for the primary endpoint at Week 16. In addition, participants who do not return for evaluation at Week 16 will be considered nonresponders at Week 16.

In this primary analysis, the number and proportion of participants who achieve a HiSCR at Week 16 will be summarized for each treatment group. To address the primary objective, a CMH chi-squared statistic stratified by baseline weight (≤95 kg, >95 kg) and baseline Hurley stage at an alpha level of 0.05 will be used for each of the following hypotheses:

- 1. Guselkumab Regimen 1 (1200 mg IV q4w x 3 → 200 mg SC q4w) versus placebo in HiSCR at Week 16.
- 2. Guselkumab Regimen 2 (200 mg SC q4w x 3 \rightarrow 200 mg SC q4w) versus placebo in HiSCR at Week 16.

The study is considered positive if at least one of the hypotheses is tested as significant.

[figure not shown]

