9.4.2.2. Major Secondary Analyses

The major secondary analyses are:

- The change from baseline in total AN count at Week 16 will be compared between each of the guselkumab groups and the placebo group.
- The change from baseline in DLQI at Week 16 will be compared between each of the guselkumab groups and the placebo group.
- The change from baseline in HS-related skin pain in the past 24 hours based on HSSD at Week 16 will be compared between each of the guselkumab groups and the placebo group.

The primary and major secondary hypotheses will be tested in the specified order and the order and procedure are shown in Figure 2.

Figure 2: Diagram for Multiple Testing Procedure for Primary and Secondary Hypotheses

With the sequential analyses specified above within each dose group vs placebo, each of the hypotheses will be tested at a 2-sided α -level of 0.05 provided that the significance is achieved for the preceding hypothesis test in the specified order shown in Figure 2. If a given comparison is not significant at the 2-sided α -level of 0.05, nominal p values will be provided for the subsequent treatment group comparisons and the subsequent treatment group comparisons will be considered as supportive.

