5.2. Analysis Specifications

5.2.1. Level of Significance

[figure not shown]
Unless otherwise specified, all statistical testing procedures will be performed at a 2-sided significance level of 0.05. This study is designed to maintain an overall Type I error of 0.1 or less for the primary analysis and major secondary analyses. Nominal p-values will be reported for other secondary analyses.

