5.2.1.1. Multiplicity Adjustment for Testing Procedures

This study has 1 primary endpoint (proportion of participants who achieved Hidradenitis Suppurativa Clinical Response (HiSCR) at Week 16) and 3 major secondary endpoints. With 2 treatment comparisons for each of these endpoints, there are a total of 8 hypotheses to be tested.

The primary and major secondary hypotheses will be tested in the specified order and the order and procedure are shown in [Figure 2](#).

Figure 2: Diagram for Multiple Testing Procedure for Primary and Secondary Hypotheses

With the sequential analyses specified above within each dose group vs placebo, each of the hypotheses will be tested at a 2-sided α -level of 0.05 provided that the significance is achieved for the preceding hypothesis test in the specified order shown in [Figure 2](#). If a given comparison is not significant at the 2-sided α -level of 0.05, nominal p values will be provided for the subsequent treatment group comparisons within each dose group vs placebo and these comparisons will be considered as supportive.

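### Does the protocol's claim of overall Type 1 error control at alpha 0.05 misstate an either-dose success rule that carries about 9%?

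*Protocol*

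**What the plan says.** The synopsis (protocol 1.1, Efficacy Analyses) gives the purpose of the sequence, "In order to control the overall Type 1 error rate for comparisons between each guselkumab group and the placebo group", and then its form: "the primary analysis and major secondary analyses will be tested in a fixed sequence for the comparisons at an alpha level of 0.05".

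Protocol 9.4.2.1 sets out two primary hypotheses, one per regimen. Its stratified CMH test "at an alpha level of 0.05 will be used for each of the following hypotheses". The success rule follows: "The study is considered positive if at least one of the hypotheses is tested as significant".

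Protocol 9.4.2.2 describes the sequence as running inside each dose-versus-placebo comparison, each step at two-sided 0.05 and conditional on the step before. The next sentence is the stop rule. After a failed test, "nominal p values will be provided for the subsequent treatment group comparisons and the subsequent treatment group comparisons will be considered as supportive".

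SAP 5.2.1.1 repeats the scheme and states the per-dose limit again within the stop rule itself: "nominal p values will be provided for the subsequent treatment group comparisons within each dose group vs placebo". SAP 5.2.1 alone gives the overall level: "This study is designed to maintain an overall Type I error of 0.1 or less for the primary analysis and major secondary analyses".

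On power, protocol 9.2 says that with 60 per arm "there will be more than 90% power to detect a treatment difference of 30% with a significance level of 0.05". The synopsis says that this power is for each guselkumab group against placebo.

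**The concern.** Someone who reads only the synopsis sees overall error control, a fixed sequence and one alpha, 0.05. Two wrong conclusions are then possible.

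- **The level.** The reader may attach 5% to the declaration of a positive study. With two chances to win at 0.05 each and no split of alpha, the either-dose rule carries nearly twice that.
- **The structure.** The reader may picture one chain across both doses. That would hold 0.05 overall, but a failure on the first dose would leave every result for the second merely supportive. The SAP keeps the second dose as a formal test.

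At stake would be how a positive result is described, and which results count as formally tested.

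**Working it through.** **Inputs.** Allocation is 1:1:1 with 60 per arm and one placebo group (protocol 1.1, 9.2). There are two primary tests at two-sided 0.05, and the study is positive if either is significant (9.4.2.1). There are four endpoints for each of two doses, so 8 hypotheses (SAP 5.2.1.1). The interim analysis looks only for low efficacy (protocol 9.5), so it adds no Type 1 error.

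**Step 1: the plan's own power figures.** For a two-sided test with pooled variance under the null, power = Φ{[√n·d − z·√(2p̄q̄)] / √(p1q1 + p2q2)}. For 25% vs 55%, n = 60, p̄ = 0.40:

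- √60 × 0.30 = 2.324
- 1.96 × √0.48 = 1.358
- √(0.1875 + 0.2475) = 0.6595
- (2.324 − 1.358) / 0.6595 = 1.464, so power is 0.928

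The plan states 93%. The six rows of Table 1 compute to 84.1, 94.1, 98.4, 81.6, 92.8 and 98.0%, against 85, 94, 98, 82, 93 and 98% stated. These are per-comparison figures at 0.05, as the layout of the table shows.

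**Step 2: error rate of the either-dose rule.** The two statistics share the placebo arm. With equal arms their correlation is (1/n)/(2/n) = 0.5.

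- Upper bound: 0.05 + 0.05 = 0.10
- If the tests were independent: 1 − 0.95² = 0.0975
- With correlation 0.5: 1 − P(|Z1| < 1.96, |Z2| < 1.96) = 0.0907
- In favour of guselkumab only, with correlation 0.5: 0.0454, against 0.025 for one comparison

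Simulating the stratified CMH test with 60 per arm and no effect gives 0.088 to 0.091. The runs used response rates of 20 to 30%, or rates that differed between strata, and four or six strata whose sizes are assumptions.

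**Step 3: all 8 hypotheses.** A fixed sequence holds 0.05 within one dose. Two such sequences give at most 0.05 + 0.05 = 0.10. Under the global null an error on a later endpoint requires an error on HiSCR first, so the rate is again 0.0907. The SAP's 0.1 is met.

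**Step 4: can the text be read as one chain?** Under a single chain the second dose could reach significance on HiSCR only if the first already had, and a rule that either dose suffices would be pointless. Protocol 9.1 and 9.4.2.1 both contain that rule. Protocol 9.4.2.2 also puts the sequence inside each dose, in the sentence directly before its stop rule. The single-chain reading therefore survives only for someone who stops at the synopsis.

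**Step 5: what 0.05 overall would cost.** Splitting alpha equally (0.025 per dose, z = 2.241) gives (2.324 − 1.553) / 0.6595 = 1.169, or 87.9% power for 25% vs 55%. That falls below the planned 90%. A split is not the only route, since a single ordered chain would also hold 0.05, but it shows what the chosen level buys.

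**The case for a change.** The best argument for acting is that the protocol makes its own claim of control and ought to state the level that claim carries. The amendment added text to clarify the multiple-testing procedure, yet the synopsis still does not say in words that the sequence runs per dose. The SAP's stop rule is more explicit than the protocol's. A correction would take a few sentences and touch no analysis.

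Part of this stands. The protocol text does not give the overall level across doses, and the synopsis, read alone, is looser than the body. Three things limit its weight.

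- The synopsis speaks of control for comparisons of each guselkumab group with placebo. Read per dose, that is true at 0.05. Nowhere does the protocol say 0.05 across the two doses.
- Protocol sections 9 and 9.4.1 leave statistical specifics to the SAP, and the SAP supplies a level that is correct for the scheme.
- The testing diagram, Figure 2, is not shown in the copy reviewed, nor is a figure that follows the stop rule in the synopsis. Either may show the per-dose order, so their absence cannot count against the plan.

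The two-sided 9% also needs its direction. The hypotheses in protocol 9.1 are of superiority, and the chance of a false finding in that direction is about 4.5%. Comparing 9% with 5% is like for like, but about half of the 9% is placebo appearing better.

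**Conclusion.** No change follows. The arithmetic behind the concern is right: about 9.1% two-sided for the either-dose rule, about 4.5% in favour of guselkumab, and never more than 10%. But the documents do not contradict each other. The protocol sets 0.05 per hypothesis and per dose, the SAP sets 0.1 overall, and the procedure satisfies both. An overall 0.1 across two regimens is a deliberate and reasonable choice for a Phase 2 proof-of-concept study, and it is what keeps power above 90% at 60 per arm.

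The gap is one of placement: the overall level appears in the SAP and not in the protocol. An analyst following either document would run the same tests at the same levels and reach the same decisions.

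The conclusion rests on equal arms with a shared placebo group (correlation 0.5), on an interim analysis that can stop only for low efficacy, and on the written text alone, because the diagrams were not available. The 10% bound for the two per-dose sequences does not depend on the correlation.
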